We will measure Pre-NDPP costs using principles of time-driven activity based costing, ^{48,49} accounting for Lifestyle Coach and supervisor time (including salaries and benefits), supplies and other direct costs, and indirect costs (e.g., facilities and general administrative expenses). To focus on Pre-NDPP, we will exclude other costs associated with standard NDPP delivery and research-related costs (e.g., data collection solely for research purposes). To facilitate accurate estimates of personnel costs, coaches and their supervisor will track time spent on Pre-NDPP activities (e.g., training, outreach, preparing for and conducting Pre-NDPP) and report total hours for each Pre-NDPP activity quarterly. Supplies and other direct costs will also be reported quarterly. Standard cost collection guides will be used by study staff.

| Measure | easure Description Method of Collection | | | | | |
|--|--|--|---|--|--|--|
| Characteristics | | | | | | |
| Demographics | Age, gender, race/ethnicity, primary language, income, education, household composition, etc | Collected from EHR and during first study visit | BL | | | |
| Body mass index | Baseline body mass index (kg/m²) | Collected during first study visit (or within 1-2 weeks of remotely-conducted initial study visits) | | | | |
| | Main outcom | les | T | | | |
| Initial NDPP attendance | ≥1 NDPP session attended 1-25 NDPP sessions attended | Collected during NDPP delivery; | | | | |
| # of sessions attended | (including virtual vs. in-person sessions) | Note weight is also measured at an initial study assessment and at a final 12-month study visit | | | | |
| Duration in NDPP | 1-365 days of NDPP participation | (we are setting up a time for all randomized individuals to have | | | | |
| # of between-session calls completed | 1-25 between-session support calls completed | their weight measured at these study visits, for which they will | Ongoing collection | | | |
| Physical activity | Average self-reported weekly minutes at each NDPP session | receive gift cards). Participants may also text/email a picture of | | | | |
| Percent weight change | Based on a) BL to 12 months (primary outcome), and b) first to last NDPP sessions attended | their weight using a study- provided scale for in-home use if not meeting in-person for weight | | | | |
| ≥5% weight loss | Achieved at any point in the NDPP | collection. | | | | |
| | Mediators | | T | | | |

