Retention. We aim to have 400 randomized participants across arms attending ≥1 NDPP session. We established initial retention rates during our 2013-2017 NDPP delivery and Pre-NDPP pilot as described above and in Preliminary Data (e.g., 83% [n=75] of participants attended the NDPP after completing a pre-session). We expect similar rates of early retention following the initial assessment in this study. Note dropout does not impede our ability to test main effects of Pre-NDPP on NDPP attendance and weight loss as: 1) NDPP engagement is a main outcome of interest; 2) The primary outcome of percent weight loss from baseline to 12 months will be assessed by intent-to-treat (ITT) analysis. Imputation methods for missingness will be used as appropriate (see Analysis Plan). For generalizability, we will deliver NDPP with only customary retention methods: offering classes at clinics where participants receive their primary care (with an option to join classes remotely, as allowable by the CDC since 2018²³), facilitating transportation as needed (e.g., providing free parking and information about insurance-provided transportation benefits), offering make-up sessions as needed, and updating participant contact information often. To reduce both participant and study staff burden, make up sessions will be offered primarily as a pre-recorded audio and/or video of the Lifestyle Coach talking through the session content (without other participants present). Coaches will seek to follow up briefly (e.g., 10-15 minutes) with participants via phone to ensure comprehension and address remaining questions. To accommodate additional data collection required of participants in both arms of the trial (above and beyond routine care in the NDPP), we will provide compensation of \$25 for completing each of two 30-minute research assessments at the time of initial recruitment and immediately prior to attending the NDPP. We will also provide an additional \$25 for all participants to complete a final study visit for weight measurement at 12 months (which may be collected via an in-home, study-provided scale as needed).

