Description of the National Diabetes Prevention Program (for both conditions). The yearlong NDPP promotes modest weight loss through diet and physical activity. The curriculum is published by the CDC.3 We will follow CDC guidelines for implementing the standard group-based NDPP,³⁷ including 16 weekly to biweekly sessions, followed by ≥6 monthly sessions over a total of one year. The objective of NDPP is achieving ≥5% weight loss. Attending more sessions is associated with greater weight loss, 4,22 and guidelines allow NDPP sites to offer more than the minimum 22 sessions to support this goal. We will offer 25 total NDPP sessions (16 in months 1-6; 9 in months 7-12), held at the same time, day, and location in group visit rooms available at 8 neighborhood primary care clinics. There will also be an option to attend classes virtually via phone or videoconference. In light of COVID-19, in-person group classes will be offered when allowable by public health entities and Denver Health, although a virtual attendance option will remain for participants who prefer to join remotely. Two new NDPP classes will commence quarterly over 2.5 years. To minimize potential contamination, participants in the two study arms will be enrolled in separate NDPP classes. Trained, bilingual lay health educators will lead NDPP classes as Lifestyle Coaches and provide make-up sessions as needed. They will be observed by the research coordinator and/or qualitative research assistant for fidelity and to assess for potential bias in NDPP delivery. Weight is measured at each session on a high-capacity, medicalgrade scale, or by reporting their weight from a study-provided in-home scale. As required by the NDPP curriculum, participants are encouraged to achieve a weekly goal of ≥150 minutes of moderate to vigorous intensity physical activity (beginning gradually as needed). Participants are instructed to track start and stop times and report total weekly activity minutes at the following session. The most recent CDC curriculum also

encourages a low-fat diet, but does not require monitoring of dietary adherence.^{3,32} Lifestyle Coaches conduct support calls between sessions to support engagement and health behavior change, address individual questions and concerns, and remind participants about upcoming sessions.

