
Pre-NDPP cost and ROI. We will first calculate Pre-NDPP cost as the average expense of each presession delivery based on personnel time, supplies and other direct costs, and indirect costs. We will then determine the projected ROI of Pre-NDPP from both provider and payer perspectives. For NDPP providers, ROI will be calculated as the additional payment expected from payers as a result of potentially improved retention and weight loss of Pre-NDPP participants minus the average pre-session cost and divided by presession cost. For common reference, payments will be based on the Medicare reimbursement schedule for achievement of NDPP attendance and weight loss milestones. 10 We will compare the average expected reimbursement for participants in both study arms to measure additional payments that may be attributed to Pre-NDPP. We will also conduct a sensitivity analysis by calculating the projected ROI for varying numbers of Pre-NDPP participants with varying demographic characteristics (e.g., race/ethnicity, income), and with other available NDPP payment schedules (e.g., Maryland Medicaid⁶⁰). Sensitivity analysis results will inform Pre-NDPP sustainability by identifying the number of participants needed per pre-session to achieve a positive ROI, the extent to which moderators identified in Hypothesis 2.3 affect ROI, and the extent to which different payment models affect ROI. From the perspective of NDPP payers, ROI will account for the expected reduction in direct healthcare expenditures as a result of covering Pre-NDPP through an additional payment to NDPP providers, as calculated over a 3-year horizon. ROI will be the reduction in projected expenditures minus the average pre-session cost and divided by pre-session cost. Estimates of change in direct healthcare expenditures will be based on the impact of Pre-NDPP on weight loss from Hypothesis 1.1, the known relationship between weight loss and T2D incidence²⁰, and the difference in expenditures for individuals with prediabetes or T2D over a 3-year horizon.⁶¹ This timeline requires discounting of expected reductions in years 2 and 3 expenditures for which we will apply a standard 3% discount rate. We will also conduct a sensitivity analysis by varying the number of Pre-NDPP participants, their characteristics, and the discount rate. To be conservative, cost and ROI is based on all Pre-NDPP participants, regardless of NDPP attendance.

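### Provider ROI counts the payments from better retention but sets any resulting increase in per-participant NDPP coach time to zero

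*Combined protocol and SAP*

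**What the plan says.** The provider formula is in section IV.F, Aim 3, under Pre-NDPP cost and ROI. It starts from the return: "ROI will be calculated as the additional payment expected from payers as a result of potentially improved retention and weight loss". From this the plan subtracts one cost only, that of the average pre-session, and the same cost serves as the divisor. The additional payment is the difference between arms in average expected reimbursement, with the Medicare milestone schedule as the reference. The cost term is narrow: "We will first calculate Pre-NDPP cost as the average expense of each presession delivery", built from personnel time, supplies, other direct costs and indirect costs.

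The boundary on costs is set in section IV.A (Data collection for Aim 3) and repeated in IV.C (Observations and interviews): "To focus on Pre-NDPP, we will exclude other costs associated with standard NDPP delivery and research-related costs". In the same place, "coaches and their supervisor will track time spent on Pre-NDPP activities"; the examples given are training, outreach, preparation and delivery of the pre-session.

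Standard NDPP delivery includes coach work done person by person. Section IV.C, in the description of the NDPP: "Lifestyle Coaches conduct support calls between sessions to support engagement and health behavior change". Table 1 records 1 to 25 completed calls per participant, and IV.A treats call completion as a marker of engagement and treatment dose. For make-up sessions, IV.C (Retention) adds: "Coaches will seek to follow up briefly (e.g., 10-15 minutes) with participants via phone".

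The provider sensitivity analyses vary the number of participants, their demographic mix and the payment schedule. They do not vary NDPP delivery cost. The economic limitations in section IV.E do not mention it either.

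**The concern.** The return and the cost are drawn on different boundaries. The return includes money earned because participants stay longer in the NDPP and lose more weight there. The cost stops at the pre-session. Delivery cost would cancel between arms if both arms used the NDPP equally, but Hypothesis 1.2 predicts that they will not, and part of the return depends on that difference.

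Group-class time is not the problem: a scheduled class runs whether or not one more person attends. What can rise is individual coach time, chiefly support calls.

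Aim 3 hypothesises a projected ROI large enough to justify the cost of Pre-NDPP, and the plan will report how many participants per pre-session give a positive ROI. Both are meant to inform suppliers deciding on uptake. If the intervention adds individual coach time, both will look more favourable than what a supplier would experience.

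**Working it through.** The documents give no ROI, payment, wage or call-length figure, so there is no stated result to reproduce. The direction follows from algebra; only a rough time comparison is possible for size.

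**1. ROI.** Put A, C and V on the same per-participant basis.

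- Planned: ROI = (A − C)/C. Break-even at A = C.
- With V netted from the return: ROI = (A − V − C)/C. Break-even at A = C + V.
- Overstatement: (A − C)/C − (A − V − C)/C = V/C, positive whenever V > 0.

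Illustration with an assumed A/C = 3, so planned ROI = 2.0:

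| V/C (assumed) | ROI with V netted |
|---|---|
| 0.25 | 1.75 |
| 0.5 | 1.5 |
| 1 | 1.0 |
| 2 | 0 |

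**2. Participants needed per pre-session.** Suppose a pre-session costs F regardless of attendance and each participant brings additional payment A. The planned rule gives a positive ROI when n > F/A. With V deducted it needs n > F/(A − V), which is larger by the factor A/(A − V). With A/C = 3 and V/C = 0.5, this is 3/2.5 = 1.2.

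**3. Possible extra call time.** Section III gives the pilot contrasts:

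- Attendance: 49.3 − 35.0 = 14.3 percentage points. Of the 25 sessions offered (IV.C), 0.143 × 25 = 3.6 sessions.
- Duration: 196.3 − 96.5 = 99.8 days. At the Table 1 maximum of 25 calls a year, 99.8/365 × 25 = 6.8 call slots. This is a ceiling, since 25 is the top of the recorded range.

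Assume one call per extra session or slot and 5 to 15 minutes per call. The factor 0.8 reflects the roughly 20% early attrition expected in IV.C (Recruitment).

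| Basis | 5 min | 10 min | 15 min |
|---|---|---|---|
| Sessions: 3.575 × min × 0.8 | 14 | 29 | 43 |
| Duration: 6.84 × min × 0.8 | 27 | 55 | 82 |

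Extra coach minutes per participant: about 14 to 82, before any change in make-up follow-ups.

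**4. Pre-session contact time that is counted.** A pre-session lasts 60 to 90 minutes (IV.C). The research coordinator assists at all of them, so one or two staff may be costed. Attendance is taken as 18 (smallest group in Table 2) to 25 (half of 50 recruits per quarter).

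- Lowest: 60 × 1/25 = 2.4 minutes per participant.
- Highest: 90 × 2/18 = 10 minutes per participant.

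C also includes training, outreach, preparation, supervisor time, supplies and indirect cost, none of which is quantified. If these brought the total to five times contact time, an assumed factor, C would be equivalent to 12 to 50 minutes. That range overlaps 14 to 82.

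**The case against.** The exclusion is declared openly, and it is the right boundary for the stand-alone cost of Pre-NDPP. That stands, and the fix leaves it alone. It does not carry over to a net return made up of NDPP payments.

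V might be close to zero. Nothing says that support calls stop when someone leaves; they also serve as reminders, and if coaches keep calling those who miss sessions, call time need not rise with retention. Make-up follow-ups are triggered by missed sessions, so better attendance could reduce them. The pilot gains come from a non-randomised comparison with earlier participants and may not recur. All of this bears on the size of V and could bring it to zero or below. It is a reason to measure V, not to fix it at zero by design.

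The plan describes its ROI as conservative, but that remark concerns counting Pre-NDPP participants who never attend the NDPP, which is a different matter.

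This is also a projected measure in a secondary aim. It does not touch the primary outcome, randomisation or power. Because completed calls are recorded in any case, a later sensitivity analysis with an assumed call length would still be possible. That limits the harm, but actual minutes are hard to recover unless logged at the time.

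**Conclusion.** The point holds conditionally. As written, provider ROI is overstated by V/C whenever Pre-NDPP produces a net increase in individual NDPP coach time. Break-even is then A = C + V, and the reported number of participants needed per pre-session is too low. This rests on V being positive, which Hypothesis 1.2 and the treatment of calls as an engagement measure make plausible but do not prove.

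A reader might infer that the omitted cost is larger than the counted one, since 14 to 82 minutes of calls looks large beside 2.4 to 10 minutes of contact. The documents do not support that. Contact time is only part of C, the upper end of the call range uses a ceiling of 25 calls, and the ranges overlap once an allowance is made for the other components. The supportable statement is that V may be comparable to C and cannot be assumed negligible.

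Nor do the documents settle whether V belongs in the denominator as well. Dividing by C + V changes the ROI value (1.0 rather than 1.5 at A/C = 3 and V/C = 0.5) but not the break-even, so netting V from the return is enough to correct the decision threshold.

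**What to change.** Keep the exclusion for fixed group-class cost and for the stand-alone Pre-NDPP cost. For provider ROI only:

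- Use (A − V − C)/C. V is the between-arm difference, per randomised participant, in coach time on support calls and make-up follow-ups, multiplied by coach cost per unit of time. Put A and C on the same per-participant basis.
- Take completed calls from the counts already collected in both arms. Add make-up counts and average minutes per call and per make-up follow-up to the coach time log, by arm.
- Add minutes per contact to the provider sensitivity analysis, and recompute the number of participants needed per pre-session with V included.
- Report the currently planned figure alongside, labelled as return before incremental NDPP delivery cost.

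The cost is a few extra entries in an existing log and one change to a formula. The downside for the sponsor is that the reported ROI may be less favourable.

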Aim 1: To evaluate clinical effectiveness of the Pre-NDPP intervention. We will recruit 500 diverse, predominately low-income patients with elevated diabetes risks (e.g., prediabetes) in the Denver Health safety net healthcare system. We will conduct a RCT to compare NDPP attendance and weight loss outcomes between participants randomized to receive the Pre-NDPP enhancement vs. direct enrollment into the NDPP (usual care). Pre-sessions, led by trained Lifestyle Coaches, will focus on providing information on diabetes risks and locally available resources to reduce risk, including the NDPP. Coaches will use MI techniques to help participants identify an actionable plan to reduce risk, such as attending NDPP sessions, and guide participants in identifying barriers and possible solutions that would enable participation. Pre-NDPP participants and usual care NDPP participants will be assigned to separate NDPP classes to prevent contamination of Pre-NDPP effects. We will collect data on demographics, NDPP outcomes (primary outcome is percent weight loss), potential mediators, implementation factors, and cost. We hypothesize that Pre-NDPP participants will have greater engagement and weight loss compared to those who are directly enrolled into the program (usual care).

Aim 2: To examine mediators and moderators of Pre-NDPP outcomes. We will explore potential mediators (perceived risk for developing diabetes and self-efficacy and readiness for weight control) and key sociodemographic variables (race/ethnicity and income level) as potential moderators of intervention effectiveness that are important to understand for future uptake by stakeholders. We hypothesize that a) Pre-NDPP will increase perceived risk, self-efficacy, and readiness, which will mediate relationships between presession treatment and NDPP outcomes, and that b) race/ethnicity and income level will moderate Pre-NDPP effectiveness.

Aim 3: To evaluate the implementation factors of Pre-NDPP. In preparation for potential future dissemination, we will evaluate implementation factors following a RE-AIM framework⁸, including a qualitative evaluation of pre-sessions from a Lifestyle Coach, clinic provider/personnel, and patient perspective. We will

also evaluate the cost of adding pre-sessions to NDPP delivery and projected return on investment (ROI). We hypothesize that Pre-NDPP will be implementable and yield sufficient projected ROI to justify its cost.

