E. Potential Scientific Problems. This study is powered on percent weight loss; more limited power is expected to evaluate Pre-NDPP effectiveness among demographic subgroups and mediators/moderators. Although we do not anticipate difficulty meeting recruitment goals via provider referrals, we can identify more eligible participants as needed from an EHR-derived patient registry. Regarding implementation, delivery is limited to a single healthcare system, yet in a variety of different clinics and following CDC standards for NDPP delivery. Economic analysis limitations include reliance on literature-derived estimates of projected cost savings and the relationship between weight loss and T2D incidence. It is possible there will be limited or no effect of Pre-NDPP in an RCT, but pilot results are strong and any clinically meaningful benefit may be worthwhile given Pre-NDPP is expected to be a relatively low-resource intervention. Financial incentives may in fact lead to better outcomes than obtained in previous observational study, but are only offered for study-related assessments and appropriately sized.

F. Data Analysis Plan.

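### The payer ROI leaves out the extra NDPP milestone payments that the provider ROI counts as income, so it overstates the payer's return if Pre-NDPP raises those payments

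*Combined protocol and SAP*

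**What the plan says.** The plan defines two returns on investment under Aim 3 (IV.F, Pre-NDPP cost and ROI).

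- **Provider.** "ROI will be calculated as the additional payment expected from payers as a result of potentially improved retention and weight loss" among Pre-NDPP participants, less the average pre-session cost, divided by that cost. Payments follow the Medicare schedule of attendance and weight-loss milestones. The increment comes from the randomised comparison: "We will compare the average expected reimbursement for participants in both study arms to measure additional payments that may be attributed to Pre-NDPP".
- **Payer.** "ROI will be the reduction in projected expenditures minus the average pre-session cost and divided by pre-session cost". The expenditure reduction is projected over three years: "Estimates of change in direct healthcare expenditures will be based on the impact of Pre-NDPP on weight loss from Hypothesis 1.1", combined with the published link between weight loss and type 2 diabetes incidence and with the difference in spending between prediabetes and diabetes.
- **Payer sensitivity analysis.** "We will also conduct a sensitivity analysis by varying the number of Pre-NDPP participants, their characteristics, and the discount rate".

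Pre-session cost covers delivery of the pre-session only. The cost-collection text in IV.A leaves out the costs of standard NDPP delivery. The limitations in IV.E read: "Economic analysis limitations include reliance on literature-derived estimates of projected cost savings and the relationship between weight loss and T2D incidence".

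**The concern.** The extra milestone payments are a transfer from payer to provider. The plan attributes them to Pre-NDPP and credits them to the provider, but does not charge them to the payer who makes them.

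The omission has a direction under the trial's own hypotheses. Aim 1 states: "We hypothesize that Pre-NDPP participants will have greater engagement and weight loss compared to those who are directly enrolled into the program". Attendance and weight loss are the two things that trigger milestone payments, so if Aim 1 succeeds the payer's outlay rises.

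Aim 3 goes on to "hypothesize that Pre-NDPP will be implementable and yield sufficient projected ROI to justify its cost". Payers such as Medicare, commercial insurers and employers are named as possible supporters of dissemination, and Table 1 uses ROI as an indicator of sustainability. A payer ROI that leaves out part of the payer's cost could support a coverage decision that the full accounts would not.

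**Working it through.** The plan states no ROI, cost, payment or savings amount, so there is no figure to reproduce. The check compares the two formulas algebraically.

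**Inputs, all per participant**
- S: projected 3-year reduction in direct healthcare expenditure (IV.F).
- C: pre-session cost (IV.F).
- A: between-arm difference in expected milestone reimbursement (IV.F, provider ROI).

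**Is A inside another term?** S is based on the weight-loss effect, diabetes incidence and the prediabetes/diabetes spending difference, and none of these is an NDPP payment. C is pre-session delivery cost. The payer sensitivity analysis varies participant number, participant characteristics and the discount rate. The provider sensitivity analysis also varies the payment schedule; the payer analysis does not. So A does not enter the payer calculation at any point.

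**Formulas**
- Provider, as written: (A − C)/C = A/C − 1.
- Payer, as written: (S − C)/C.
- Payer with A counted, denominator C: (S − C − A)/C. The overstatement is A/C, which equals the provider ROI plus 1.
- Payer with A counted, denominator full outlay: (S − C − A)/(C + A). The overstatement is S/C − S/(C + A) = S·A/[C(C + A)].

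**At true payer break-even**, S = C + A, both corrected forms give 0% and the written formula gives A/C:

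| A/C | Payer ROI as written | Corrected payer ROI | Provider ROI |
|---|---|---|---|
| 0.1 | 10% | 0% | −90% |
| 0.5 | 50% | 0% | −50% |
| 1.0 | 100% | 0% | 0% |
| 1.5 | 150% | 0% | +50% |

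**Away from break-even** (assumed ratios):

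| S/C | A/C | As written | Corrected, denominator C | Corrected, denominator C + A |
|---|---|---|---|---|
| 1.5 | 1.0 | 50% | −50% | −25% |
| 2 | 0.1 | 100% | 90% | 82% |
| 3 | 0.5 | 200% | 150% | 100% |
| 3 | 1.0 | 200% | 100% | 50% |
| 3 | 1.5 | 200% | 50% | 20% |
| 5 | 0.5 | 400% | 350% | 233% |

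First row: as written, 1.5 − 1 = 0.5; with A counted, 1.5 − 1 − 1 = −0.5, and −0.5/2 = −0.25.

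**Wrong sign.** The written formula is positive when S > C. The payer gains only when S > C + A. The two disagree when C < S < C + A.

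**The case against.** The strongest counter-reading is that A is already included. The payer text speaks of covering Pre-NDPP by a further payment to providers, and milestone payments could be seen as part of a payer's direct expenditure, so S might be meant as a net figure. The text does not support this. The payment mentioned is the one that covers Pre-NDPP, the formula subtracts only pre-session cost, and the stated inputs to S concern diabetes incidence and its costs. If a net figure was intended, the formula still has to say so.

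It can also be argued that a return on the pre-session payment alone is a legitimate, narrower quantity. It is, if labelled that way. The plan presents it as the payer's ROI.

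Several qualifications stand:
- A payer without performance-based milestones has A = 0 and no bias.
- The Background allows that pre-sessions may work mainly as a screen. A averaged over all Pre-NDPP participants could then be small.
- S and A both rise with weight loss. A larger A widens the range in which the sign is wrong, but does not by itself make a wrong sign more likely.
- The loss is a loss over the plan's 3-year horizon. The Background cites benefits lasting up to 15 years, so a longer-run loss is not shown.
- This is a projected Aim 3 output, and A could still be added at reporting because its data are collected anyway.

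These points limit the size and reach of the error. They do not supply the missing term.

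**Conclusion.** The concern holds. The payer formula omits a payer cost that the plan itself attributes to Pre-NDPP and already plans to estimate. With C as denominator, the overstatement is exactly A/C, so any positive provider ROI (A > C) implies a payer overstatement of more than 100 percentage points. The sign is wrong when C < S < C + A. Where S is large relative to A, the sign is right and only the size is inflated.

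The direction rests on A > 0, which the trial hypothesises but has not shown. A negative A would reverse the bias. The size in money cannot be given, because it depends on S, C and A and the documents state none of them. Only the Aim 3 payer ROI is affected. The primary outcome, power and type I error are not. The formula should be corrected before the ROI is reported.

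**What to change.** 1. Subtract A in the payer numerator, using the between-arm difference in expected reimbursement from the provider ROI, under the payment schedule of the payer in question. Pre-session cost can stay as the stand-in for the payment that covers Pre-NDPP.
2. State the denominator: (S − C − A)/C or (S − C − A)/(C + A). Sign and break-even point are the same, but the size away from break-even differs, as the tables show.
3. Put S, C and A on one unit. The plan defines C per pre-session delivered and reimbursement per participant, so C has to be divided by the number of participants per pre-session. The provider ROI needs the same conversion.
4. Carry A through the payer sensitivity analysis, including the alternative payment schedules already planned for the provider.

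The change takes a few lines in the analysis plan and needs no new data. The price is a less favourable payer ROI if A is positive, and a choice of denominator that must be fixed in advance.
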